## **2.2. Study Objectives**

*To investigate the following items in patients treated with this drug under post-marketing routine uses.*

*[1] Occurrence of adverse events, including the investigation of following factors:*

*Background factors that may affect the occurrence of liver disorder including VOD/SOS, myelosuppression, infection, hemorrhage, and Grade  $\geq 3$  events based on Common Terminology Criteria for Adverse Events (CTCAE) version 4.0; and risk factors for early death in HSCT recipients after treatment with this drug.*

*[2] Effectiveness (hematologic response rate, survival)*

## **3. INTERIM AND FINAL ANALYSES**

In this study, interim analyses for periodic safety update reports will be performed periodically. Among analysis items defined in this SAP, only the analysis items necessary for periodic safety reports will be analyzed at the time of interim analysis. In addition, a final analysis to support the re-examination application will be performed. All analyses specified in this SAP will be performed at the time of the final analysis.

## **4. HYPOTHESES AND DECISION RULES**

### **4.1. Statistical Hypotheses**

Since this study is not a confirmatory study, statistical testing should be positioned as exploratory. The p-value of a statistical test will be evaluated as a descriptive statistic and the significance level will not be specified, but a threshold may be set in a post-hoc manner for screening purpose.

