5. MILESTONES

Milestone	Planned date
Start of investigation period	Start date of releasing BESONSA to the market
Start of data collection (registration date of the first patient)	2 July 2018
End of investigation period	5 years after the start date of releasing BESONSA to the market*
End of data collection (release date of the database)	May 2024
Final study report	October 2024

*: See Section 8.4. "Planned Study Period."

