8.10.2. Rationale

A total of 176 patients was chosen as the number of patients evaluable for risk factors related to the onset of VOD/SOS. The incidence of VOD/SOS was 12.3% (26/212 patients) in clinical studies (Studies B1931022 and B1931010).

A sample size enabling to evaluate the effect of risk factors related to the onset of VOD/SOS, which were identified in clinical studies, under actual conditions of use, and to search other risk factors was selected. Assuming the true incidence of 12.3% in all patients, a true relative risk associated with the onset of events in subgroups of 3.0 (equivalent to the incidence in the high and low risk groups being assumed to be 18.5% and 6.2%, respectively), and a ratio of the patients in each group being 1:1, when defining a probability of detecting a statistically significant relative risk as power, a sample size of 176 patients would provide power of 80.4% in a (two-sided) chi square test with a significance level of 0.1.

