## 1. REVISION HISTORY

Version/ Date/ Author(s)	Summary of Changes/Comments
6.0 02-Sep-2024 PPD	
 
○ Section 5.4: Some subgroup factors and their categories were added.
 
○ Section 8.2.2: Histogram classes were changed.
 
○ Section 8.2.2: Analysis of correlation between age and patient characteristics was added.
 
○ Section 8.2.3.1: The factors explored in the "Exploration of factors associated with the occurrence of VOD/SOS" were changed.
 
○ Section 8.2.3.4: Specifications and factors for subgroup analyses of adverse drug reactions were added.
 
○ Section 8.2.3.4: Analysis of adverse events was deleted from the subgroup analyses of adverse drug reactions.
 
○ Section 8.2.4.1: The categorization for the summary of hematologic response data by cycle was changed.
 
○ Section 8.2.4.4: Analysis of deaths and causes of death were added.
 
○ Section 9: Some listings were added and specifications were changed.
 
○ Editorial revisions
 

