*A sample size of 176 patients was selected so as to be able to evaluate potential risk factors associated with the occurrence of VOD/SOS. In clinical studies (Studies B1931022 and B1931010), the incidence of VOD/SOS was 12.3% (26/212 patients).*

*The sample size was determined so as to be able to confirm the effects of the risk factors identified in clinical studies on the occurrence of VOD/SOS in routine clinical practice and explore other potential risk factors. Assuming that the true incidence in the overall population is 12.3%, the true relative risk of the onset of events in subgroups is 3.0 (corresponding to assuming that the incidence in the high-risk group and in the low-risk group is 18.5% and 6.2%, respectively), and the ratio of the sample size in each subgroup is 1:1, the sample size of 176 patients has 80.4% power in a chi-square test with a significance level of 0.1 (two-sided), assuming the probability of detecting a statistically significant relative risk as the power.*

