#### 8.1.3. Binary variables

For binary variables, patients falling into each binary category will be summarized in terms of frequency (n) and proportion. If a confidence interval (CI) is determined for a proportion, the two-sided 95% CI will be determined using the exact method.

For a comparison of proportion between subgroups, the risk ratio (RR) and its 95% CI will be determined. In addition, the RRs and their 95% CIs will be graphically presented.

For statistical tests, Fisher's exact test will be performed to test correlations in nominal scale data, and Cochran-Armitage test (exact method) to test correlations in ordinal scale data. If, however, it is difficult to use the exact method, chi-square test or Cochran-Armitage test with normal approximation will be used as an alternative to the exact method.

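### The 80.4% power behind the 176 patients is for a chi-square test at 0.1, but the SAP sets no level, allows a post hoc screening threshold and plans exact tests, so the figure describes no planned analysis

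*SAP*

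**What the plan says.** The sizing text in Protocol 8.10.2 defines power as the probability of finding a statistically significant relative risk for VOD/SOS. It assumes an overall incidence of 12.3%, a relative risk of 3.0 and two groups of equal size, "equivalent to the incidence in the high and low risk groups being assumed to be 18.5% and 6.2%, respectively". It concludes that "a sample size of 176 patients would provide power of 80.4% in a (two-sided) chi square test with a significance level of 0.1". SAP 2.1 repeats this as protocol text.

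The analysis sections do not carry it forward:

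- SAP 4.1 calls the testing exploratory and the p-values descriptive, and adds that "the significance level will not be specified, but a threshold may be set in a post-hoc manner for screening purpose". SAP 4.2 has no decision rules.
- SAP 8.1.3 assigns Fisher's exact test to nominal factors and the exact Cochran-Armitage test to ordinal ones. The chi-square test, or the normal-approximation trend test, is used only where the exact method is impracticable.
- On intervals, SAP 8.1.3 states: "For a comparison of proportion between subgroups, the risk ratio (RR) and its 95% CI will be determined".
- SAP 8.2.3.1 applies these methods to the VOD/SOS factor exploration, first for all VOD/SOS and then for VOD/SOS in patients transplanted after starting the drug.

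The SAP revision history records that version 6.0, dated 2 September 2024, changed the factors in the section called "Exploration of factors associated with the occurrence of VOD/SOS". Protocol section 5 plans the database release for May 2024 and the final report for October 2024.

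**The concern.** The sample size rests on a test and a level that no analysis section adopts. A reader who takes 80.4% as the chance that the VOD/SOS screen picks up a threefold risk is misled twice: the planned test is a different and more conservative one, and the level is open.

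The open level matters more than the test. SAP 4.1 does not merely leave p-values descriptive. It reserves a screening cut-off, which is a selection rule, and lets it be set once the p-values are known. Neither the sensitivity of the screen nor the number of chance findings to expect among the flagged factors can then be stated in advance. Evaluating VOD/SOS risk factors is a stated objective, and SAP section 3 says that the final analysis supports the re-examination application, so which factors are singled out will be read with some weight.

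**Working it through.** **Inputs.** From Protocol 8.10.2: 176 patients split 1:1 (88 per group), overall incidence 12.3%, relative risk 3.0, two-sided chi-square at 0.1. With equal groups, the low-risk rate is 2 × 12.3% / (1 + 3) = 6.15% and the high-risk rate is 18.45%. The protocol rounds these to 6.2% and 18.5%.

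**Step 1: reproduce the plan's figure.** With the pooled variance under the null hypothesis and no continuity correction,

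power = Φ[(Δ − z·SE0) / SE1]

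- Δ = 0.1845 − 0.0615 = 0.123
- SE0 = √(2 × 0.123 × 0.877 / 88) = 0.0495
- SE1 = √[(0.1845 × 0.8155 + 0.0615 × 0.9385) / 88] = 0.0486
- z = 1.645 at two-sided 0.10

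This gives Φ(0.854) = 80.4%. The rounded rates give 80.2%. The sponsor's arithmetic is right.

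**Step 2: the same formula at other levels.** Power is 89.0% at 0.20, 70.3% at 0.05 and 46.3% at 0.01. This is the range that a post hoc choice of threshold leaves open.

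**Step 3: the test that is planned.** For Fisher's exact test, add the binomial probabilities Bin(x; 88, 0.1845) × Bin(y; 88, 0.0615) over all tables (x, y) whose Fisher p-value is at or below the level. For the risk ratio, do the same over tables where log RR ± z·√(1/x − 1/88 + 1/y − 1/88) excludes 0. The SAP names no interval method for the risk ratio; this log-scale one is my assumption.

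| Analysis, 88 versus 88 | Level 0.10 | Level 0.05 |
|---|---|---|
| Chi-square, formula of Step 1 | 80.4% | 70.3% |
| Chi-square, exact enumeration | 82.0% | about 72% |
| Fisher's exact test | 75.2% | 65.1% |
| Risk-ratio interval excludes 1 | 81.0% (90% interval) | 68.7% (95% interval) |

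Naming 0.10 therefore does not by itself restore 80.4%. With Fisher's test the figure is about 75%.

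**Step 4: how many tests.** SAP 8.2.3.1 lists 17 factor codings (age in three codings) for all VOD/SOS. The same list is applied to VOD/SOS with transplant after the drug, where the factor for transplant after the drug cannot vary, leaving 16. A further 13 transplant-related codings follow. Total: 17 + 16 + 13 = 46.

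If no factor had any effect, the expected number of false signals is at most 46 × 0.10 = 4.6, or 46 × 0.05 = 2.3 at 0.05. Expected counts do not need independent tests. Exact tests are conservative: with 12.3% in both groups of 88, Fisher's test rejects in 6.2% of samples at nominal 0.10, and 46 × 0.062 ≈ 2.8. That last figure is only an illustration, because groups will differ in size and the trend tests were not modelled.

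**Step 5: where the power figure cannot apply.** Of the 46 tests, 16 + 13 = 29 are confined to patients transplanted after the drug. A calculation with 88 versus 88 uses all 176 patients, so it does not describe those 29 unless every patient is transplanted.

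**Step 6: dates.** The planned database release (May 2024) precedes SAP 6.0 (2 September 2024). The current factor lists do not show which VOD/SOS factors changed in that version.

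**The case against.** The strongest reply is that this is declared policy. The SAP says openly that the study is not confirmatory, that p-values are descriptive and that there are no decision rules. A power figure with no matching decision is then a planning device, and Protocol 8.12 lets the SAP modify the outlined analyses. Most of this stands: an exploratory safety survey needs no formal significance level. It does not cover the post hoc threshold, because choosing which factors to flag is a selection even when it is called screening.

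Four stronger readings are tempting, and the documents do not support them.

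- A reader might infer that 80.4% is wrong. It reproduces.
- A reader might take the 95% intervals as a commitment to testing at 0.05. They are a general reporting convention for proportions; the 69% shows only what someone reading significance from them would get.
- A reader might infer that a movable cut-off could hide a VOD/SOS signal. SAP 8.2.3.1 commits to counts, proportions and a test for every listed factor, and only a risk ratio may be left out, for categories under 10 patients. The cut-off affects which factors are highlighted, not which are shown.
- A reader might infer that the factor list was changed with results in hand. May 2024 is a planned date, no actual release date is given, and the version log discloses the change. The dates support calling the change late, and no more.

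**Conclusion.** The point holds in this limited form and is worth correcting. The 80.4% is a valid planning figure for a balanced two-level factor in the whole safety set, tested by chi-square at two-sided 0.1. No analysis section plans that test at that level. For Fisher's exact test, the figure is about 75% at 0.10 and 65% at 0.05. Alongside this, the clause allowing a post hoc threshold leaves the screen's error rate undefined without need, since a level is already on record from the sizing.

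These figures assume the protocol's rates, a 1:1 split and 176 analysable patients. Factors that are unbalanced or have more than two categories will differ. The issue affects how flagged factors are interpreted; the planned tabulations remain usable as they are.

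**What to change.** 1. In SAP 4.1, delete the post hoc threshold. Name two-sided 0.10, the level used for sizing, as the exploratory screening level for the VOD/SOS factor analysis, and keep the statement that p-values are descriptive and non-confirmatory.
2. In SAP 2.1 or 4.1, state that 80.4% is a planning figure for a 1:1 factor in the whole safety set under chi-square. Then either give about 75% for Fisher's exact test or adopt chi-square for this screen. State that the figure does not apply to the transplant-only analyses.
3. Report the number of factors tested beside any factor flagged, with the bound of about 4.6 chance findings in 46 tests at 0.10, fewer with exact tests.
4. Mark the VOD/SOS factors changed in SAP 6.0 as late changes.

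Showing 90% intervals beside the 95% ones is optional.

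The cost is SAP wording, a table note and a marker on some rows; no new data are needed. The sponsor gives up the freedom to choose a cut-off later. Fixing 0.10 now is itself late, but it is the only level that the documents already record, so it is unlikely to look tailored to the results.

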#### 4.2. Statistical Decision Rules

Not applicable.

### 5. ANALYSIS SETS

#### 5.1. Safety Analysis Set

The safety analysis set (SAS) is defined as the full analysis set (FAS) that is as close as possible to all patients treated with this drug. Specifically, the SAS consists of all registered or reported patients except those who meet any of the following conditions:

- a. The case report form could not be collected at all. (Indicated as "CRF not collected" in the survey report.)
- b. There was a violation or flaw in the study contract. (Indicated as "Contract violation/flaw" in the survey report.)
- c. There was a violation in the registration. (Indicated as "Invalid registration" in the survey report.)
- d. Administration of the survey drug was not reported at all. (Indicated as "No dosing information" in the survey report.)
- e. The case report form at the original hospital before patient transfer has not been fixed. (Indicated as "No dosing information - dosing information unconfirmed") \* This condition applies only to cases where information of the original hospital and that of the transferred hospital are linked. If the original hospital refuses continued survey or information from the original hospital becomes uncollectible, this exclusion condition is considered not met (the patient will not be excluded because of this exclusion criterion).
- f. Information on adverse events was not reported at all - no visits after the first prescription. (Indicated as "No information on adverse events - no visits" in the survey report.)
- g. Information on adverse events was not reported at all - there is a visit(s) after the first prescription but no record of information. (Indicated as "No information on adverse events - no record" in the survey report.)

For details of each criterion other than e, see the Guidance for Adoption/Rejection Criteria for Analysis Populations and Handling of Data in Special Investigation.

#### 5.2. Effectiveness Analysis Set

The effectiveness analysis set (EAS) consists of all patients in the SAS except those who meet any of the following conditions:

- h. Effectiveness cannot be appropriately evaluated because some of the necessary conditions for evaluating effectiveness are missing. (Indicated as "Unable to evaluate effectiveness" in the survey report.)
- i. Disease is outside the scope of survey. (Indicated as "Disease outside the scope" in the survey report.)  
This survey includes the following exclusion criterion: Patients whose condition is not relapsed or refractory CD22+ acute lymphocytic leukemia (ALL)

### 5.3. Other Analysis Sets

#### 5.3.1. Safety analysis set with informed consent

The safety analysis set with informed consent (SASIC) is defined as all registered or reported patients with informed consent, excluding those who meet any of the conditions in Section 5.1.

#### 5.3.2. Effectiveness analysis set with informed consent

The effectiveness analysis set with informed consent (EASIC) is defined as all patients in the SASIC, excluding those who meet any of the conditions in Section 5.2.

### 5.4. Subgroups

Subgroup analyses of safety will be performed for the following patient characteristics. The subgroups defined for each background factor are shown in the squared brackets [] with the reference for the calculation of risk ratio/difference being underlined:

- Age [< 15 years, ≥ 15 to < 65 years, ≥ 65 years]
- Age [< 18 years, ≥ 18 to < 55 years, ≥ 55 years]
- Age [< 15 years, ≥ 15 to < 40 years, ≥ 40 years]
- Disease name [Relapsed CD22+ acute lymphocytic leukemia (ALL), refractory CD22+ ALL, other ALL, other]
- Chromosome karyotype [normal, t (4;11), unknown]
- Chromosome karyotype [Philadelphia chromosome positive, negative, unknown]\* Philadelphia chromosome is considered positive if the chromosome karyotype is t(9;22).
- Hepatic impairment [absent, present] {According to the Procedure of Extracting Patients with Hepatic Impairment/Renal Impairment in Post-Marketing Surveillance and its Attachment, the version of Medical Dictionary for Regulatory Activities Terminology (MedDRA) used for analysis should be followed.}
- Renal impairment [absent, present] (According to the Procedure of Extracting Patients with Hepatic Impairment/Renal Impairment in Post-Marketing Surveillance and its Attachment, the MedDRA version used for analysis should be followed.)
- Medical history (past) - VOD/SOS [absent, present]
- Medical history (past) - Graft versus host disease (GVHD) [absent, present]
- Medical history (past) - Hepatitis or hepatic disease [absent, present]

- Medical history (present) - VOD/SOS [absent, present]
- Medical history (present) - GVHD [absent, present]
- Medical history (present) - Hepatitis or hepatic disease [absent, present]
- Eastern Cooperative Oncology Group performance status (ECOG PS) before the start of this drug [0, 1,  $\geq 2$ , not performed]
- Aspartate aminotransferase (AST) and alanine aminotransferase (ALT) levels immediately before the start of this drug [ $\leq 1.5 \times$  the institutional upper limit of normal range (IULN), either  $> 1.5 \times$  IULN, not performed]
- $\gamma$ -glutamyl transpeptidase ( $\gamma$ -GTP) level immediately before the start of this drug [ $\leq 50$  IU/L,  $> 50$  IU/L, not performed]
- Total bilirubin level immediately before the start of this drug [ $\leq$  the institutional upper limit of normal range (IULN),  $>$  IULN, not performed]
- Hemoglobin level immediately before the start of this drug [ $< 10$  g/dL,  $\geq 10$  g/dL, not performed]
- White blood cell count immediately before the start of this drug [ $\leq 4000/\text{mm}^3$ ,  $\geq 4000/\text{mm}^3$ , not performed]
- Neutrophil count immediately before the start of this drug [ $\leq 2000/\text{mm}^3$ ,  $\geq 2000/\text{mm}^3$ , not performed]
- Platelet count immediately before the start of this drug [ $< 10 \times 10^4/\mu\text{L}$ ,  $\geq 10 \times 10^4/\mu\text{L}$ , not performed]
- Peripheral blast count immediately before the start of this drug [ $\leq 1000/\mu\text{L}$ ,  $> 1000/\mu\text{L}$ , not performed]
- Myeloblast count immediately before the start of this drug [ $\leq 50\%$ ,  $> 50\%$ , not performed]
- Salvage line of the induction treatment with this drug [Initial induction, 1st, 2nd, 3rd or later]
- HSCT before the start of this drug [not performed, performed]

Subgroup analyses of safety will be performed also for the following factors:

- HSCT after the start of this drug [not performed, performed]
- Type of the first HSCT after the start of this drug [autologous transplant, allogeneic hematopoietic stem cell transplant with myeloablative conditioning, allogeneic hematopoietic stem cell transplant with nonmyeloablative conditioning, unknown]
- Donor of the first HSCT after the start of this drug [alternative donor, matched related donor]
- Conditioning with alkylating agent for the first HSCT after the start of this drug [ $\leq 1$  agent (including no conditioning),  $\geq 2$  agents]
- Conditioning with busulfan for the first HSCT after the start of this drug [not performed (including no conditioning), performed]
- ECOG PS before conditioning for the first HSCT after the start of this drug [0, 1,  $\geq 2$ , not performed]
- AST and ALT levels before conditioning for the first HSCT after the start of this drug [ $\leq 1.5 \times$  the institutional upper limit of normal range (IULN), either  $> 1.5 \times$  IULN, not performed]
- $\gamma$ -GTP level before conditioning for the first HSCT after the start of this drug [ $\leq 50$  IU/L,  $> 50$  IU/L, not performed]

- Total bilirubin level before conditioning for the first HSCT after the start of this drug [≤ institutional upper limit of normal range (IULN), > IULN, not performed]
- Hemoglobin level before conditioning for the first HSCT after the start of this drug [< 10 g/dL, ≥ 10 g/dL, not performed]
- Platelet count before conditioning for the first HSCT after the start of this drug [< 10 × 10^4/µL, ≥ 10 × 10^4/µL, not performed]
- Peripheral blast count before conditioning for the first HSCT after the start of this drug [≤ 1000 /µL, > 1000 /µL, not performed]
- Myeloblast count before conditioning for the first HSCT after the start of this drug [≤ 50%, > 50%, not performed]
- Time from the date of final dose of this drug to the date of the first HSCT after the start of this drug [< 4 weeks, ≥ 4 weeks to < 8 weeks, ≥ 8 weeks to < 12 weeks, ≥ 12 weeks to < 16 weeks, ≥ 16 weeks]
- Treatment cycles [1 cycle, 2 cycles, 3 cycles, 4 cycles, 5 cycles, 6 cycles, > 6 cycles]
- Treatment cycles [≤ 3 cycles, ≥ 4 cycles]
- Dosing of > 1.8 mg/m^2 per cycle [absent, present] (Considered to be present, if there is a cycle of > 1.8 mg/m^2 per cycle during the treatment period.)
- Pregnancy [absent, present] \* Pregnancy during the treatment period. Limited to cases in which information on pregnancy is collected
- Best overall response [complete remission (CR) or complete remission with incomplete hematologic recovery (CRI), progression or relapse, indeterminate/other, not performed]
- Minimal residual disease (MRD) [negativity achieved, negativity not achieved, test not performed]
  - \* Irrespective of the result of best overall response.
- Best overall response and MRD [CR/CRI achieved and negativity achieved, CR/CRI achieved and negativity not achieved, progression/relapse and negativity achieved, progression/relapse and negativity not achieved] \* "Indeterminate/other" and "not performed" are excluded.
- Adverse drug reactions that occurred during the treatment period - liver disorder as a safety specification [absent, present]

Subgroup analyses of hematologic response and MRD will be performed for the following patient characteristics and other factors:

- Age [< 15 years, ≥ 15 to < 65 years, ≥ 65 years]
- Age [< 18 years, ≥ 18 to < 55 years, ≥ 55 years]
- Age [< 15 years, ≥ 15 to < 40 years, ≥ 40 years]
- Disease name [Relapsed CD22+ acute lymphocytic leukemia (ALL), refractory CD22+ ALL]
- Chromosome karyotype [normal, t (4;11), unknown]
- Chromosome karyotype [Philadelphia chromosome positive, negative, unknown]\* Philadelphia chromosome is considered positive if the chromosome karyotype is t(9;22).
- Hemoglobin level immediately before the start of this drug [< 10 g/dL, ≥ 10 g/dL, not performed]
- Platelet count immediately before the start of this drug [< 10 × 10^4/µL, ≥ 10 × 10^4/µL, not performed]

- Peripheral blast count immediately before the start of this drug [ $\leq 1000/\mu\text{L}$ ,  $> 1000/\mu\text{L}$ , not performed]
- Myeloblast count immediately before the start of this drug [ $\leq 50\%$ ,  $> 50\%$ , not performed]
- Salvage line of the induction treatment with this drug [Initial induction, 1st, 2nd, 3rd or later]
- HSCT before the start of this drug [not performed, performed]
- Pregnancy [absent, present] \* Pregnancy during the treatment period. Limited to cases in which information on pregnancy is collected

Subgroup analyses of overall survival (OS) will be performed for the following patient characteristics and other factors:

- Age [ $< 15$  years,  $\geq 15$  to  $< 65$  years,  $\geq 65$  years]
- Age [ $< 18$  years,  $\geq 18$  to  $< 55$  years,  $\geq 55$  years]
- Age [ $< 15$  years,  $\geq 15$  to  $< 40$  years,  $\geq 40$  years]
- Disease name [Relapsed CD22+ acute lymphocytic leukemia (ALL), refractory CD22+ ALL]
- Chromosome karyotype [normal, t (4;11), unknown]
- Chromosome karyotype [Philadelphia chromosome positive, negative, unknown]\* Philadelphia chromosome is considered positive if the chromosome karyotype is t(9;22).
- Hemoglobin level immediately before the start of this drug [ $< 10\text{ g/dL}$ ,  $\geq 10\text{ g/dL}$ , not performed]
- Platelet count immediately before the start of this drug [ $< 10 \times 10^4/\mu\text{L}$ ,  $\geq 10 \times 10^4/\mu\text{L}$ , not performed]
- Peripheral blast count immediately before the start of this drug [ $\leq 1000/\mu\text{L}$ ,  $> 1000/\mu\text{L}$ , not performed]
- Myeloblast count immediately before the start of this drug [ $\leq 50\%$ ,  $> 50\%$ , not performed]
- Salvage line of the induction treatment with this drug [Initial induction, 1st, 2nd, 3rd or later]
- HSCT before the start of this drug [not performed, performed]
- Pregnancy [absent, present] \* Pregnancy during the treatment period. Limited to cases in which information on pregnancy is collected
- Best overall response [CR or CRi, progression or relapse, indeterminate or other, not performed]
- Best overall response [CR, CRi]\* "Progression", "relapse", "indeterminate/other" and "not performed" are excluded.
- MRD [negativity achieved, negativity not achieved, test not performed] \* Irrespective of the result of best overall response.
- Best overall response and MRD [CR/CRi achieved and negativity achieved, CR/CRi achieved and negativity not achieved, progression/relapse and negativity achieved, progression/relapse and negativity not achieved] \* "Indeterminate/other" and "not performed" are excluded.

